#### 4. Populations for Analysis

The analysis populations will consist of participants as defined below.

The Screened population will consist of all rollover participants with chronic migraine from lead-in 3101-303-002 study and De Novo EM participants, who signed informed consent for this extension study.

The Safety population will consist of all participants who receive at least 1 dose of study intervention (atogepant) in this extension study.

The mITT population will consist of all participants who received at least 1 dose of study intervention (atogepant) in this study, an evaluable baseline (in this study for De Novo EM Participants or in the lead-in study for the rollover participants), and had at least 1 evaluable post-baseline 4-week period of eDiary data in this extension study.

The listing of serious adverse events and participants who died will be provided for the Screened population.

## 5. Statistical Analyses

### 5.1. General Considerations

- Efficacy endpoints will be analyzed descriptively based on the mITT population.
- Safety endpoints will be performed using the Safety population.
- Continuous variables will be summarized by number of participants with observed values (n), mean, standard deviation (SD), median, 1st and 3rd quartiles (Q1, Q3), minimum (min), and maximum (max).
- Categorical variables will be summarized by number of participants with observed values, events (n), frequency count (n1), and percentage of participants with observed values.
- Partial dates will be treated as missing in computation or in variable derivation unless specified otherwise, but will be listed in the data listings as they appear on the eCRF.
- For monthly endpoints, baseline is defined as assessments during the last 28 days of baseline period in the lead-in study for 3101-303-002 rollover participants, and the last 28 days of the screening/baseline period for De Novo EM Participants. For efficacy endpoints that are assessed at clinical visits, baseline is defined as the last non-missing efficacy assessment before the first dose of study intervention in the lead-in study (3101-303-002) for 3101-303-002 Completers, and the last non-missing efficacy assessment before the first dose of study for De Novo EM Participants. For each of the clinical, laboratory, vital sign, and ECG parameters, the baseline is defined as the baseline value in the lead-in study (3101-303-002) for 3101-303-002 Completers, and the last nonmissing safety assessment before the first dose of study drug for De Novo EM Participants.
- The change from baseline values will be computed as the post-baseline value minus the baseline value.
- Study intervention is treatment administered (atogepant 60 mg QD).
- All statistical analysis will be performed using SAS version 9.4 or higher.
- Medical Dictionary for Regulatory Activities (MedDRA), Version 27.0 or higher, will be used to code adverse events and medical history.
- WHO Drug Global B3 (v.202403 or higher) will be used to code medications.

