3.1 Structure

This is a multicenter, open-label, 52-week, long-term safety extension study conducted in Japan and will enroll at least 170 participants from approximately 25 sites, to meet a target of a minimum of 100 participants exposed to atogepant at 1 year. Participants will be treated with atogepant 60 mg once daily.

The study will consist of a 52-week open-label treatment period and a 4-week safety follow-up period for all participants. For De Novo EM Participants only, a 4-week screening/baseline period will be required.

The study will recruit 2 cohorts:

3101-303-002 Completers:

Japanese participants may directly rollover from Study 3101-303-002 (Phase 3 CM study); hereinafter referred to as the lead-in study. As such, participants will have Visit 7 from the

lead-in study function as Visit 1 for this study after the participant signs the informed consent. After Visit 1, study visits will occur every 4 weeks for the duration of the study. An EOS Visit will occur 4 weeks after the last dose of atogepant.

Note, there may be participants who complete Visit 7 in the lead-in study before extension Study 3101-306-002 has been initiated. Those participants should complete Visit 7/ET and Visit 8/EOS Visit (including discontinuation of study intervention) per the lead-in study Schedule of Visits and Procedures.

Depending on the timing of the initiation of this extension study, in relation to each participant's planned Visit 8 schedule in the lead-in study, Visit 1 for Study 3101-306-002 can be conducted on the same day as Visit 8/EOS Visit for the lead-in study, or soon thereafter.

1. If this extension study is initiated prior to the participant's planned Visit 8 in the lead-in study, then Visit 8/EOS Visit in the lead-in study should be conducted on the same day as Visit 1 for Study 3101-306-002.
2. If this extension study is not initiated prior to the participant's planned Visit 8 in the lead-in study (ie, there is a gap between Visit 8 and Visit 1), then Visit 8/EOS Visit should be conducted as planned per the lead-in study Schedule of Visits and Procedures. When this extension study is initiated the participant should return to the clinic as soon as possible, and Visit 1 should be conducted per the Study 3101-306-002 Schedule of Visits and Procedures.

De Novo EM Participants:

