4.3 Inclusion Criteria

4.3.1 All Participants

The following are inclusion criteria for all participants:

1. Written informed consent and participant privacy information (eg, written authorization for use and release of health and research study information and written data protection consent, per Japan regulations) obtained from the participant prior to initiation of any study-specific procedures.
2. Participants must be using a medically acceptable and effective method of birth control during the course of the entire study, as defined in Section [4.5.3](#).

4.3.2 3101-303-002 Completers

The following is inclusion criterion for 3101-303-002 Completers only:

3. Eligible participants who completed the double-blind treatment period (Visit 7) and the follow-up period (Visit 8), if applicable, depending on the timing of study initiation, of Study 3101-303-002 without significant protocol deviations (eg, noncompliance to protocol-required procedures) and who did not experience an AE that, in the investigator's opinion, may indicate an unacceptable safety risk.

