7.3 Hypothesis and Methods of Analysis

7.3.1 Safety Analyses

The safety analyses will be performed using the safety population. The safety parameters will include AEs, clinical laboratory evaluations, vital sign measurements, ECG parameters and the C-SSRS. For each of the clinical, laboratory, vital sign, and ECG parameters, the baseline value in this extension study is defined as:

- The baseline value in the lead-in study (Study 3101-303-002) for 3101-303-002 Completers.
- The last nonmissing safety assessment before the first dose of study drug for De Novo EM Participants.

Continuous variables will be summarized by the number of participants, and mean, SD, median, minimum, and maximum values. Categorical variables will be summarized by number and percentage of participants.

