### 5.2. Participant Dispositions

The number of participants in the Safety and mITT populations will be summarized; the number of participants screened will be summarized overall.

Screen-failure participants (i.e., participants who consent to participate in the study but are not subsequently treated) and the associated reasons for failure to enter into the open-label treatment period will be tabulated for all screened participants. The number and percentage of participants who enter the open-label treatment period, complete the open-label treatment period and of participants who prematurely discontinue during the open-label period will be tabulated by 3101-303-002 rollover CM participants, De Novo EM Participants, and overall for Safety population. The reasons for premature discontinuation from the open-label treatment period as recorded on the disposition page of the electronic case report forms (eCRFs) will be summarized (number and percentage). The percentage is relevant to the total number of participants in the Safety population. Similar disposition information will be presented for the safety follow-up period. All participants in the all screened population who prematurely discontinue during the open-label treatment period or the safety follow-up period will be listed by discontinuation reason.

The number of participants in the Safety population will be summarized by lead-in study treatments (placebo, Atogepant 60 mg QD, Atogepant 30 mg BID), enrollment category (3101-303-002 completer (3101-303-002 Visit 7 completer, Visit 8 completer, Completer with Gap prior to start) and De Novo EM participants), and overall.

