## 5.5. Other Analyses

### 5.5.1. Subgroup Analyses

#### Efficacy Subgroup Analyses

For all efficacy and health outcome endpoints, subgroup analyses will be performed by 3101-303-002 Completers or De Novo EM Participants and overall.

For the following efficacy endpoints, separate figures will be presented by 3101-303-002 Completers or De Novo EM Participants. The figures for over time change during the 12-Week Double-Blind treatment period and the 52-Week Open-label treatment period for 3101-303-002 CM Completers in mITT population will also be presented, for the following efficacy endpoints.

- Change from baseline in monthly migraine days at each monthly period
- Change from baseline in monthly headache days at each monthly period
- Change from baseline in monthly acute medication use days at each monthly period

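### For Completers who had placebo in the lead-in, the safety baseline falls nominally 12 weeks or more before the first atogepant dose, so pre-atogepant change enters the baseline-dependent laboratory, vital sign and ECG outputs

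*SAP*

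**What the plan says.** Protocol 7.3.1 sets the safety baseline for rollover participants as "The baseline value in the lead-in study (Study 3101-303-002) for 3101-303-002 Completers". SAP 5.1 repeats it for laboratory, vital sign and ECG parameters ("the baseline is defined as the baseline value in the lead-in study (3101-303-002) for 3101-303-002 Completers"), and SAP Table 6-10 applies it. De Novo participants instead use their last value before the first dose in this study.

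The Completer cohort mixes three lead-in arms: SAP 5.2 counts participants by "lead-in study treatments (placebo, Atogepant 60 mg QD, Atogepant 30 mg BID"). SAP 5.5.1 gives the lead-in a "12-Week Double-Blind treatment period", and Protocol 4.3.2 admits only participants who "completed the double-blind treatment period (Visit 7) and the follow-up period (Visit 8), if applicable". Protocol 3.1 allows entry at lead-in Visit 7, at Visit 8, or later ("ie, there is a gap between Visit 8 and Visit 1").

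Three further rules matter:

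- Table 6-10 starts the Completers' Week 4 open-label window on Day 1, against Day 2 for De Novo participants.
- SAP 6.4.4 uses every postbaseline assessment to determine PCS values. It also words baseline as the latest assessment preceding the first dose of study treatment, without saying which study.
- SAP 5.5.1 splits safety results into Completers, De Novo and overall. Lead-in arm appears only as a head count in SAP 5.2.

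**The concern.** The lead-in baseline is a pre-atogepant value for all Completers, but it is the last such reference only for those randomised to atogepant. For the placebo arm it is followed by about 12 weeks without atogepant, and sometimes by a gap as well. A later reference is already collected: Protocol 8.4.2.1 schedules laboratory tests, vital signs and, for Completers, an ECG at Visit 1, with dispensing listed last.

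Safety is the primary objective and the study has no control arm, so change from baseline carries most of the weight for these parameters. A weight change that arose on placebo and persists is tabulated with changes on atogepant. The error can also run the other way. A placebo participant who was PCS at lead-in baseline, normal at Visit 1 and PCS again on atogepant drops out of both numerator and denominator wherever a non-PCS baseline is required. No planned safety table by lead-in arm would show either effect.

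**Working it through.** The plan gives no figure to reproduce here. Its sample size is set by regulatory exposure requirements, and its only relevant total adds up (140 + 30 = 170). The check is a timeline, followed by a sorting of the outputs.

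**1. Time off atogepant within the change interval.** Inputs: 12 weeks of double-blind treatment (SAP 5.5.1); G = weeks from lead-in Visit 7 to extension Visit 1, which is 0 for direct rollover and otherwise not stated; w = open-label week. For a lead-in placebo Completer:

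share = (12 + G) / (12 + G + w)

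| G (weeks) | Week 4 | Week 12 | Week 24 | Week 52 |
|---|---|---|---|---|
| 0 (direct rollover) | 12/16 = 75% | 12/24 = 50% | 12/36 = 33% | 12/64 = 19% |
| 4 (assumed) | 16/20 = 80% | 16/28 = 57% | 16/40 = 40% | 16/68 = 24% |
| 26 (assumed) | 38/42 = 90% | 38/50 = 76% | 38/62 = 61% | 38/90 = 42% |

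These are shares of elapsed time, not of the change observed. The 12 weeks are nominal, because lead-in visit windows are not in the documents.

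**2. Number affected.** The documents give neither the lead-in allocation nor the number of placebo rollovers. Assuming one quarter, one third or one half of 140 Completers:

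- 140 × 1/4 = 35 (20.6% of 170)
- 140 × 1/3 = 46.7, about 47 (27.5% of 170)
- 140 × 1/2 = 70 (41.2% of 170)

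**3. Which outputs use the baseline.**

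| Output | Uses the lead-in baseline? |
|---|---|
| Change from baseline in laboratory, vital sign and ECG values | Yes |
| Weight PCS (7% change, no observed-value criterion, Table 6-5) | Yes, on change alone |
| Blood pressure and pulse PCS | Yes, but an observed-value limit must also be met |
| QTcF increase > 30 and > 60 msec | Yes |
| PCS tables requiring a non-PCS baseline (laboratory, ECG, orthostatic) | Yes, for who is counted |
| ECG shift table | Yes |
| Treatment-emergent adverse events | No; anchored to first open-label dose (SAP 5.4.3) |
| QTcF > 450, > 480, > 500 msec | No |
| Hepatic multiples of ULN (Table 6-4) | No |

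**4. The Day 1 window.** Day 1 is the date of the first open-label dose (SAP 6.4). If that is also the date of Visit 1, the pre-dose Visit 1 values fall in the Completers' window, and SAP 6.4.4 makes them eligible for PCS. In by-visit summaries a later Week 4 value would normally replace them, since the last visit in a window is used. That does not help the ECG, which is not scheduled again until Week 12. The Day 1 window can also admit a pre-dose value to the hepatic multiples, although those need no baseline.

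**5. Illustration for weight.** Assume a normal distribution, a 52-week SD of 3%, 4% or 5%, and variance growing in proportion to time. P(|change| ≥ 7%) = 2·P(Z > 7/SD), with SD multiplied by √(64/52) for the longer interval.

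| Assumed SD | 52 weeks | 64 weeks | Excess | Among 47 |
|---|---|---|---|---|
| 3% | 2.0% | 3.5% | 1.6 points | 0.7 participants |
| 4% | 8.0% | 11.5% | 3.5 points | 1.6 participants |
| 5% | 16.2% | 20.7% | 4.5 points | 2.1 participants |

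Excesses are taken before rounding. These are probabilities at one time point. The planned table counts anyone with at least one PCS value during the study, so they indicate scale and do not estimate the tabulated rate.

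**The case against.** The choice is deliberate and consistent. Protocol 7.3.1, SAP 5.1 and Table 6-10 agree, and the SAP change log records a move to the lead-in baseline to align with other atogepant extension studies. It suits both atogepant arms. The study is descriptive with no statistical hypothesis, and for a direct rollover 52 of the 64 weeks are uncontrolled under either baseline. All of that stands, and it is why the 5.1 tables should stay. Alignment still does not give placebo Completers a reference close to their first atogepant dose.

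Visit 1 criteria also limit carry-over. Protocol 8.9 withdraws Completers with ALT, AST or bilirubin above ULN (Gilbert's disease excepted for bilirubin), low albumin, or QTcF above 450 msec (males) or 470 msec (females). Exclusion criterion 4 uses sitting pressure limits of 160 and 100 mm Hg, below the high PCS limits of 180 and 105. This stands for those parameters. It does not cover weight, pulse, low blood pressure or most other laboratory values. A QTcF increase over 30 msec can also occur below the absolute limits.

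A reader might infer that the safety results as a whole attribute placebo-period events to atogepant. The documents do not support that: adverse events are anchored to the first open-label dose, and a change that resolved before Day 1 is not counted at all. Nor should the gap be called unlimited. No maximum is stated, but Protocol 3.1 asks participants to return as soon as possible once the extension starts, and SAP 5.2 counts gap Completers separately.

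**Conclusion.** The point holds for lead-in placebo Completers and for the baseline-dependent outputs listed above. Before Week 12 of open-label treatment, most of a direct rollover's change interval is time off atogepant; by Week 52 it is about a fifth, and more with a gap. Those shares rest on the nominal 12 weeks. The count of 35 to 70 participants rests on an assumed placebo share.

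The likely effect on any one table is modest. On the assumed weight figures it is about 0.7 to 2.1 extra participants among 47. Masking of real changes is possible, but the documents give no basis for sizing it. The Day 1 window is a separate defect: it can turn a value taken before the first open-label dose into a postbaseline PCS finding.

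This does not invalidate the planned tables. It justifies supportive ones, because safety is the primary objective and the data already exist.

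**What to change.** 1. Keep the tables based on SAP 5.1.
2. Add supportive change-from-baseline, PCS, QTcF-increase and ECG shift tables in which baseline is the last value before the first atogepant dose in either study. For lead-in placebo Completers this is the pre-dose Visit 1 value; for the two atogepant arms it stays in the lead-in.
3. In Table 6-10, exclude pre-dose Day 1 values from the Completers' postbaseline window. Without this, the same Visit 1 value could serve as both baseline and postbaseline in the new tables.
4. Reword baseline in SAP 6.4.4 so that it names the study and agrees with 5.1.

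The cost is a repeat run of existing programs with a second baseline variable, and slightly more output. No new data are needed.

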### 5.2. Participant Dispositions

The number of participants in the Safety and mITT populations will be summarized; the number of participants screened will be summarized overall.

Screen-failure participants (i.e., participants who consent to participate in the study but are not subsequently treated) and the associated reasons for failure to enter into the open-label treatment period will be tabulated for all screened participants. The number and percentage of participants who enter the open-label treatment period, complete the open-label treatment period and of participants who prematurely discontinue during the open-label period will be tabulated by 3101-303-002 rollover CM participants, De Novo EM Participants, and overall for Safety population. The reasons for premature discontinuation from the open-label treatment period as recorded on the disposition page of the electronic case report forms (eCRFs) will be summarized (number and percentage). The percentage is relevant to the total number of participants in the Safety population. Similar disposition information will be presented for the safety follow-up period. All participants in the all screened population who prematurely discontinue during the open-label treatment period or the safety follow-up period will be listed by discontinuation reason.

The number of participants in the Safety population will be summarized by lead-in study treatments (placebo, Atogepant 60 mg QD, Atogepant 30 mg BID), enrollment category (3101-303-002 completer (3101-303-002 Visit 7 completer, Visit 8 completer, Completer with Gap prior to start) and De Novo EM participants), and overall.

## **5.3. Efficacy Endpoint Analyses and Health Outcome Measures**

### **5.3.1. Definition of Endpoints**

Since the primary objective of this open-label extension study is to assess the safety and tolerability over 52 weeks of atogepant treatment, efficacy endpoints are not classified as primary, secondary, or additional.

Efficacy endpoints are listed below, and will be analyzed descriptively.

- Change from baseline in monthly migraine days at each monthly period (i.e., each consecutive 4-week period)
- Change from baseline in monthly headache days at each monthly period
- Change from baseline in monthly acute medication use days at each monthly period  $\geq 25\%$ ,  $\geq 30\%$ ,  $\geq 50\%$ ,  $\geq 75\%$ , and 100% improvement (decrease) in monthly migraine days at each monthly period
- Change from baseline in monthly triptan use days at each monthly period
- Change from baseline in monthly moderate/severe headache days at each monthly period
- Change from baseline in monthly severe headache days at each monthly period

- Change from baseline in monthly cumulative headache hours at each monthly period
- At least a 5-point improvement (decrease) from baseline in total HIT-6 score at each monthly period
- Change from baseline in the HIT-6 total score at each monthly period
- Rating of "much better" or "very much better" at Weeks 12, 24, 36, 48, and 52 assessed by the PGIC
- Change from baseline in percent work time missed, percent impairment while working, percent overall impairment, and percent activity impairment due to migraine at each monthly period as assessed by the WPAI:MIGRAINE
- Change from baseline in EQ-5D-5L descriptive system index score at each monthly period
- Change from baseline in the EQ-5D-5L VAS score at each monthly period
- Participants reporting "satisfied" or "extremely satisfied" with study medication for migraine prevention at each monthly period
- Change from baseline in monthly Performance of Daily Activities domain score of the AIM-D at each monthly period
- Change from baseline in monthly Physical Impairment domain score of the AIM-D at each monthly period
- Change from baseline in monthly AIM-D total score at each monthly period
- Change from baseline in monthly activity level at each monthly period
- Change from baseline in monthly activity limitation at each monthly period
- Change from baseline in MIDAS absenteeism score (Questions 1, 3, and 5) at Weeks 12, 24, 36, 48, and 52
- Change from baseline in MIDAS presenteeism score (Questions 2 and 4) at Weeks 12, 24, 36, 48, and 52
- Change from baseline in the MIDAS total score at Weeks 12, 24, 36, 48, and 52
- Change from baseline in PGI-S at each monthly period
- Change from baseline in the MSQ v2.1 Role Function-Restrictive domain score at Weeks 12, 24, 36, 48, 52, and 56
- Change from baseline in the MSQ v2.1 Role Function-Preventive domain score at Weeks 12, 24, 36, 48, 52, and 56
- Change from baseline in the MSQ v2.1 Emotional Function domain score at Weeks 12, 24, 36, 48, 52, and 56

All efficacy endpoints listed above will be summarized descriptively. In addition, for the primary endpoint of the lead-in 3101-303-002 study (Change from baseline in monthly migraine days at

each monthly period) and for the key secondary endpoints of the lead-in 3101-303-002 study (Change from baseline in monthly headache days at each monthly period, Change from baseline in monthly acute medication use days at each monthly period,  $\geq 50\%$  improvement (decrease) in monthly migraine days at each monthly period, change from baseline in MSQ v2.1 Role Function Restrictive Domain at each monthly period, change from baseline in monthly Performance of Daily Activities domain score of the AIM-D at each monthly period, change from baseline in the Physical Impairment domain score of the AIM-D at each monthly period, change from baseline in the HIT-6 total score at each monthly period), point estimates and 95% CIs will be provided. The 95% CI for the continuous endpoints will be based on a mixed-effects model for repeated measures (MMRM). The model will include visit (derived as month) as a categorical fixed effect, and the baseline score, baseline-by-visit interaction as covariates. Restricted maximum likelihood method will be used. An unstructured covariance matrix will be used to model the covariance of within-participant repeated measurements. If the model does not converge, then simplified covariance structures will be used to fit the model in the following order: (1) Toeplitz and (2) compound symmetry. The Kenward Roger approximation ([Kenward 1997](#)) will be used to estimate the denominator degrees of freedom. Each treatment effect will be estimated by the least square mean along with the corresponding standard error and 95% confidence interval. The analysis will be performed based on all post-baseline values using only the observed cases without imputation of missing values. The 95% CI for percent improvement (decrease) in monthly migraine days at each monthly period will be based on the normal approximation to the binomial.

On a daily basis during the open-label treatment period, participants are to record into an eDiary information on the daily total duration of headache, headache specific characteristics and symptoms, the worst pain severity, and use of any acute headache pain medication. Participants will be able to report headache data, including absence of headache, for the day of the eDiary report and for the day immediately prior to the day of the eDiary report.

For analysis purpose, change from baseline will be calculated for consecutive 28-day periods beginning with study Day 1 (i.e., Weeks 1-4, 5-8 and 9-12, corresponding to Days 1-28, 29-56 and 57-84, etc.), where Day 1 is the first dose date of the open-label study treatment.

